1. OBJECTIVE

The objective of this post marketing surveillance is to further gather local data on the safety and efficacy of Brexpiprazole (Rexulti™) Film-coated Tablet in the treatment of schizophrenia and adjunctive therapy of MDD.

2. METHODS

2.1. DESIGN OF THE PMS

This is a post marketing surveillance of 8 weeks duration, on 300 male or female patients diagnosed to have schizophrenia and MDD in the Philippines.

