Treatment Indication(s)	
 • For the treatment of schizophrenia. • Adjunctive therapy to antidepressants for the treatment of major depressive disorder (MDD) 		
Objective(s)	To provide post marketing surveillance data on the safety and efficacy of Brexpiprazole (Rexulti™) Film-coated Tablet for schizophrenia and adjunctive therapy of major depressive disorder (MDD) in the Philippines.		
Study Design			
Center	Multi-center		
Blinding	Open		
Control	Active		
Design	Single Group		
Subject Population			
Planned # of subject	A total of 300 subjects will be included in the trial.		
Gender	Male and Female		
Age range	Adults (18 years old and above)		
Healthy subjects or treatment condition	Treatment condition		
Test Product, Dose, Mode of Administration			
Brand name (API)	Rexulti™	Administration route	Per Orem (PO)
Dosage form	Film-coated Tablet	Dose, regimen	Once a day
Criteria for Evaluation			
Primary Outcome Variables	Safety Assessment: Safety of Brexpiprazole (Rexulti™) Film-coated Tablet will be evaluated based on the reported AE's per assessment.		
Secondary Outcome Variables	Efficacy Assessment: Efficacy of Brexpiprazole (Rexulti™) Film-coated Tablet will be evaluated using the Clinical Global Impression (CGI) Scale : CGI – Severity - Numbers and proportions of responders (defined as patients with CGI severity (CGI-S) score of 1 (normal, not at all ill), 2 (borderline mentally ill), 3 (mildly ill), 4 (moderately ill), 5 (markedly ill), 6 (severely ill), 7 (among the most extremely ill patients)) CGI – Improvement - Numbers and proportions of responders (defined as patients with CGI improvement (CGI-I) score of 1 (very much improved), 2 (much improved), 3 (minimally improved), 4 (no change), 5 (minimally worse), 6 (much worse), 7 (very much worse))		
Study Duration			
Treatment duration	8 weeks		
Further Study Details			
Assessments will be done upon initiation, (Baseline visit), 4 weeks later (Visit 2), until completion of the study week 8 (Study Completion). Demographic information and vital signs will be collected.			

INTRODUCTION

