Schizophrenia is a serious mental disorder in which people interpret reality abnormally. Schizophrenia may result in some combination of hallucinations, delusions, and extremely disordered thinking and behavior that impairs daily functioning, and can be disabling. Depression is a mood disorder that causes a persistent feeling of sadness and loss of interest. It is also called as major depressive disorder or clinical depression which affects how you feel, think and behave and can lead to a variety of emotional and physical problems.¹

Brexpiprazole (Rexulti™) is used to treat the symptoms of schizophrenia. It is also used with an antidepressant to treat depression when symptoms cannot be controlled by an antidepressant alone. Brexpiprazole (Rexulti™) is an atypical antipsychotics or second generation antipsychotics. It works by changing the activity of certain natural substances in the brain.

Brexpiprazole (Rexulti™) has partial agonist activity at serotonergic 5-HT_{1A} and dopaminergic D₂ receptors, as well as antagonist activity at serotonergic 5-HT_{2A} receptors. The drug also has activity at noradrenergic receptors. It is available as tablets in the following strengths: 0.25, 0.5, 1, 2, 3, and 4 mg under the brand name Rexulti™.

For schizophrenia, the proposed starting dose is 1 mg once daily for 4 days, increasing to 2 mg for 3 days, and then 4 mg once daily (after Day 7) based on clinical response and tolerability. For adjunctive treatment of major depressive disorder (MDD), the proposed starting dose is 0.5 or 1 mg once daily, increasing to a target dose of 2 mg once daily based on clinical response and tolerability.

The main objective of developing this post marketing surveillance is to monitor the safety and efficacy of the drug in the treatment of schizophrenia and major depressive disorder. Another objective is to enhance their chance for early recovery, eventual reintegration to the society and improved quality of life.

Efficacy and tolerability of Brexpiprazole (Rexulti™) Film Coated Tablet

For the treatment of Schizophrenia

The efficacy of Brexpiprazole (Rexulti™) in the treatment of adults with schizophrenia was demonstrated in two 6-week, randomized, double-blind, placebo-controlled, fixed-dose clinical trials in patients who met DSM-IV-TR criteria for schizophrenia.

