2.2. PROCEDURES

Based on his clinical decision, the attending physician will enroll patients with schizophrenia and MDD to the program. The attending physician will explain to the patient or his legal guardian the purpose of the PMS and will obtain the patient or legal guardian's consent that Brexpiprazole (Rexulti™) Film-coated Tablet will be administered.

Data on the safety aspects of Brexpiprazole (Rexulti™) Film-coated Tablet will be collected in terms of adverse events. Efficacy will be measured using the Clinical Global Impression (CGI) Scale:

CGI-Severity

- Numbers and proportions of responders (defined as patients with CGI severity (CGI-S) score of 1 (normal, not at all ill), 2 (borderline mentally ill), 3 (mildly ill), 4 (moderately ill), 5 (markedly ill), 6 (severely ill), 7 (among the most extremely ill patients))

CGI-Improvement

- Numbers and proportions of responders (defined as patients with CGI improvement (CGI-I) score of 1 (very much improved), 2 (much improved), 3 (minimally improved), 4 (no change), 5 (minimally worse), 6 (much worse), 7 (very much worse) after the first and last Brexpiprazole (Rexulti™) Film-coated Tablet dose. Assessments will be done upon initiation, (Baseline visit), and 4 weeks later (Visit 2), until completion of the study week 8 (Study completion). Demographic information and vital signs will be collected.

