3. MANAGEMENT AND REPORTING OF SAFETY INFORMATION

3.1. DEFINITION OF TERMS

Safety information	Information from any source containing one or more of the following concepts: 
▪ Adverse Events▪ Special Situations▪ Off label use▪ Device Vigilance Information
Adverse Event (AE)	Any untoward medicinal occurrence in a patient or

	
clinical study subject administered a medicinal product and which does not necessarily have a causal relationship with this treatment (see Annex IV, ICH-E2A guideline).
 
An adverse event can therefore be any unfavorable and unintended sign (e.g. abnormal laboratory finding), symptom, or disease temporally associated with the use of a medicinal product, whether or not it is considered causally related to the medicinal product.

Special Situations	
Situations related to the use of an Otsuka product which may or may not be associated with an adverse event:
 
 - Maternal (pregnancy and breastfeeding) or paternal (via semen) exposure; - Exposure during breastfeeding; - Overdose/Incorrect dosage, misuse, abuse (e.g. patient sharing products); - Medication errors (e.g. patient took wrong dose); - Lack of therapeutic efficacy (e.g. the product doesn't work); - Occupational exposure (e.g.: nurse administering the product is exposed); - Cases of suspected transmission of infectious agents; - Use of suspected or confirmed falsified product(s) or quality defect of the product(s); - Withdrawal reactions; - Accidental exposure (e.g.: child takes parent's product); - Drug-drug/drug-food interactions; - Unintentional use of product in a non-approved population (e.g.: pediatric or geriatric population); - Disease progression/exacerbation of existing disease
Off-label Use	
Refers to situations where a product is intentionally used for a medical purpose not in accordance with the authorized product information. Off-label use also includes the intentional use in non-authorized population categories not indicated in the label

Device Vigilance Information	
is a death or serious injury that was or may have been attributed to a medical device component of an Otsuka product, or that a medical device component was or may have been a factor in a death or serious injury, including events occurring as a result of:
 
 - Failure, - Malfunction, - Improper or inadequate design, - Manufacture, - Labeling or instructions for use, or

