3.2. COLLECTION AND REPORTING OF SAFETY INFORMATION

All safety information that occur *during* (defined as occurring after patient enrollment until the study completion, or within 30 days of the final dose of Brexpiprazole (Rexulti™) Film-coated Tablet) the study will be documented by the physician. At each visit, the patient will be asked about any symptoms or unexpected occurrences since the last visit. All safety information, regardless of severity or relationship to the Brexpiprazole (Rexulti™) Film-coated Tablet will be reported by the physician to the OPPI using the AE Form (Otsuka Global PV Safety Information Reporting Form in Annex III) immediately or within 24 hours.

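### Do Sections 2.1 and 2.2 of the protocol enrol MDD patients whom the objective, limited to adjunctive therapy, leaves out?

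*Protocol*

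**What the plan says.** Two sets of statements in the protocol bear on who is studied.

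With the adjunctive condition:
- Synopsis, Treatment Indication(s): "Adjunctive therapy to antidepressants for the treatment of major depressive disorder (MDD".
- Synopsis, Objective(s): "for schizophrenia and adjunctive therapy of major depressive disorder (MDD) in the Philippines".
- Section 1: "in the treatment of schizophrenia and adjunctive therapy of MDD".

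Without it:
- Introduction, main-objective sentence: "to monitor the safety and efficacy of the drug in the treatment of schizophrenia and major depressive disorder".
- Section 2.1: "on 300 male or female patients diagnosed to have schizophrenia and MDD in the Philippines".
- Section 2.2: "the attending physician will enroll patients with schizophrenia and MDD to the program", on the physician's clinical decision.

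No section shown makes background antidepressant treatment a condition of entry.

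**The concern.** Sections 2.1 and 2.2 are where a site looks to see whom to enrol. Taken on their own they ask for a diagnosis and a physician's decision, and nothing else. An MDD patient on no antidepressant meets that description but falls outside the objective in the synopsis and Section 1. If sites read the text differently, the 300 patients could be a mixture, and an MDD summary that included such patients could not be presented as a result for adjunctive therapy. The word joining the two diagnoses could even be taken to require both in the same patient.

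There is also an apparent tension with safety reporting. Section 3.1 counts as off-label any case where the product is "intentionally used for a medical purpose not in accordance with the authorized product information". If the authorized indication is the one in the synopsis, the same patient could be enrolled under Section 2.2 and also be an off-label case, which Section 3.2 says "will be reported by the physician to the OPPI using the AE Form" within 24 hours. The protocol does not say how that patient then counts in the adverse event and CGI results.

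**Working it through.** No published figure needs to be reproduced. The check compares texts and then asks whether any result could go wrong.

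**1. Can both sets of statements be true?** Yes. Sections 2.1 and 2.2 say which diagnoses the patients have. The synopsis and Section 1 say how the drug is used in one of them. A contradiction would need a sentence that lets MDD patients take the drug without an antidepressant, and none is shown.

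**2. What does the rest of the protocol assume?**
- The Introduction describes use in depression as given with an antidepressant, after an antidepressant alone has failed to control symptoms.
- The starting and target doses for MDD, in the Introduction and again in the dosage subsection, are given for adjunctive use only.
- The MDD efficacy background covers adjunctive trials only.
- The main-objective sentence that omits the condition comes directly after the paragraph giving the adjunctive dose.
- The dosage subsection states the adjunctive condition once, then refers simply to patients with MDD in its hepatic and renal paragraphs. The document therefore already uses the bare diagnosis as shorthand.

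**3. Does the text require both diagnoses?** The synopsis lists the indications as two separate items. Section 1 joins its two indications with the same conjunction, where it clearly means two groups. Annex II gives one Indication/Diagnosis field with boxes to tick. The reading that requires both is strained.

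**4. Could such a patient go unnoticed?** Annex II has the site record the indication and, for any concomitant medication, its generic name, brand name, dose and frequency. The baseline page also has a psychotropic medications item. From these fields an analyst can separate MDD patients with and without a recorded antidepressant. The instructions list no start or stop dates, so the record shows that an antidepressant was noted, not that it was taken for all 8 weeks.

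**5. Does the off-label route conflict with enrolment?** No. The protocol defines off-label use and provides for its reporting, so a patient can be enrolled and also reported. The overlap depends on the authorized indication being the one in the synopsis.

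**6. How large could the effect be?** Suppose *m* MDD patients are summarised together and *k* of them have no antidepressant. Let *p*A and *p*N be the proportions with some outcome among those with and without one. The combined proportion is

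[(*m* − *k*) × *p*A + *k* × *p*N] / *m*,

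so its distance from the adjunctive proportion is (*k*/*m*) × (*p*N − *p*A). The protocol gives none of *k*, *m*, *p*A or *p*N; its only number is the total of 300. Neither size nor direction can be stated. The distance is zero if *k* = 0, and it disappears from any table that separates the two groups correctly.

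**7. Does the planned analysis force a wrong result?** Section 5 limits the analysis to descriptive statistics. It states no test and does not say that the indications are pooled. Display by indication is commonly left to the SAP, which is not shown.

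**The case for a change.** The strongest case for a change is that the enrolled population belongs in the Methods, and a reader should not have to infer it from background on the label. A case report form field is a record, not an entry rule, so being able to find a patient afterwards does not settle whether that patient should have been enrolled. The Introduction does not fully rescue the Methods either, since its own statement of the main objective drops the condition. Aligning the wording would cost a few words.

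The facts in this stand: the enrolment text is looser than the objective, and no entry condition enforces the adjunctive part. What does not follow is harm to the result. A physician who reads the whole protocol meets the adjunctive condition in the indication, the objective and the dosing before reaching Section 2. Nothing shown suggests that any site would read the text otherwise, and no number of affected patients can be derived. The remaining question, how such patients would be displayed, is one for the tables.

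**Conclusion.** No change to the plan is needed. The difference in wording is real, but Sections 2.1 and 2.2 are shorthand for a population that the synopsis, Section 1 and the general description of MDD use define as adjunctive. Investigators can fill the gap from the indication and dosing text, and analysts from the recorded indication and concomitant drugs. The effect on results cannot be quantified, and no wrong result has been shown. Aligning the sentences at some later amendment would be tidying only.

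This rests on three assumptions. Sites read Section 2 together with the indication. The case report form pages, which are not shown, follow the Annex II instructions. The SAP or the analysts do not label a mixed MDD group as adjunctive. The view would change if a page not available here expressly admitted MDD patients without an antidepressant while the results were still reported as adjunctive therapy. Nothing here bears on how any patient should be treated.

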2.2. PROCEDURES

Based on his clinical decision, the attending physician will enroll patients with schizophrenia and MDD to the program. The attending physician will explain to the patient or his legal guardian the purpose of the PMS and will obtain the patient or legal guardian's consent that Brexpiprazole (Rexulti™) Film-coated Tablet will be administered.

Data on the safety aspects of Brexpiprazole (Rexulti™) Film-coated Tablet will be collected in terms of adverse events. Efficacy will be measured using the Clinical Global Impression (CGI) Scale:

CGI-Severity

- Numbers and proportions of responders (defined as patients with CGI severity (CGI-S) score of 1 (normal, not at all ill), 2 (borderline mentally ill), 3 (mildly ill), 4 (moderately ill), 5 (markedly ill), 6 (severely ill), 7 (among the most extremely ill patients))

CGI-Improvement

- Numbers and proportions of responders (defined as patients with CGI improvement (CGI-I) score of 1 (very much improved), 2 (much improved), 3 (minimally improved), 4 (no change), 5 (minimally worse), 6 (much worse), 7 (very much worse) after the first and last Brexpiprazole (Rexulti™) Film-coated Tablet dose. Assessments will be done upon initiation, (Baseline visit), and 4 weeks later (Visit 2), until completion of the study week 8 (Study completion). Demographic information and vital signs will be collected.

3. MANAGEMENT AND REPORTING OF SAFETY INFORMATION

3.1. DEFINITION OF TERMS

Safety information	Information from any source containing one or more of the following concepts: 
▪ Adverse Events▪ Special Situations▪ Off label use▪ Device Vigilance Information
Adverse Event (AE)	Any untoward medicinal occurrence in a patient or

	
clinical study subject administered a medicinal product and which does not necessarily have a causal relationship with this treatment (see Annex IV, ICH-E2A guideline).
 
An adverse event can therefore be any unfavorable and unintended sign (e.g. abnormal laboratory finding), symptom, or disease temporally associated with the use of a medicinal product, whether or not it is considered causally related to the medicinal product.

Special Situations	
Situations related to the use of an Otsuka product which may or may not be associated with an adverse event:
 
 - Maternal (pregnancy and breastfeeding) or paternal (via semen) exposure; - Exposure during breastfeeding; - Overdose/Incorrect dosage, misuse, abuse (e.g. patient sharing products); - Medication errors (e.g. patient took wrong dose); - Lack of therapeutic efficacy (e.g. the product doesn't work); - Occupational exposure (e.g.: nurse administering the product is exposed); - Cases of suspected transmission of infectious agents; - Use of suspected or confirmed falsified product(s) or quality defect of the product(s); - Withdrawal reactions; - Accidental exposure (e.g.: child takes parent's product); - Drug-drug/drug-food interactions; - Unintentional use of product in a non-approved population (e.g.: pediatric or geriatric population); - Disease progression/exacerbation of existing disease
Off-label Use	
Refers to situations where a product is intentionally used for a medical purpose not in accordance with the authorized product information. Off-label use also includes the intentional use in non-authorized population categories not indicated in the label

Device Vigilance Information	
is a death or serious injury that was or may have been attributed to a medical device component of an Otsuka product, or that a medical device component was or may have been a factor in a death or serious injury, including events occurring as a result of:
 
 - Failure, - Malfunction, - Improper or inadequate design, - Manufacture, - Labeling or instructions for use, or

	- User error
Serious Adverse Event (SAE)	
Any adverse drug experience/event occurring at any dose which
 
 • results in death, • is life-threatening, • requires inpatient hospitalization or prolonged of existing hospitalization • results in persistent or significant disability or incapacity, • is a congenital anomaly/birth defect, • is medically significant 
Life-threatening refers to an event in which the patient was at risk of death at the time of the event; it does not refer to an event that hypothetically might have caused death if more severe.
 
A medically significant event is an important medical event (defined as a medical event(s) that may not be immediately life-threatening or result in death or hospitalization but, based on appropriate medical and scientific judgment, may jeopardize the patient/subject or may require intervention (e.g. medical, surgical) to prevent one of the other outcomes listed in the definition above) might be considered serious as well, examples of such include, but not limited to, intensive treatment in an emergency room or at home for allergic bronchospasm; blood dyscrasias; or convulsions that do not result in hospitalization; or development of drug dependency of drug abuse.

Non-Serious Adverse Event	All AEs that do not meet the definition of a serious Adverse Event (SAE) are considered non-serious AEs.
Unexpected Adverse Event/Adverse Drug Reaction	
An AE/ADR, the nature, severity, or outcome of which is not consistent with the current Investigator's Brochure (IB) or the approved labeling of the (I)MP. Class-related reactions which are mentioned in the IB, or the approved labeling but which are not specifically described as occurring under the (I)MP are also considered 'unexpected'.
 
For the determination of expectedness, an AE/ADR is considered unexpected only if it is not mentioned in the Adverse Reactions or Undesirable Effects section of the CCDS/SmPC (for MPs) or if it is not clearly described as an expected AE/ADR in section 6 of the IB (for IMPs). Exceptions are reactions related to overdose (considered unexpected if not mentioned in section Overdose) and/or interactions (considered unexpected if not mentioned in section Interaction).
 
The determination of unexpectedness is used for the purpose of expedited reporting and periodic reporting.

Date of First Receipt (DFR)	The date when an Otsuka colleague, its Alliance Company/Collaborating Company or External Service

	Provider, any third party providing services (e.g. a CRO), to or on behalf of Otsuka first becomes aware of a case/event. Email and fax headers usually record the date of receipt of communication, and it should be considered as the date of first receipt (calendar day 0).
--	---

3.2. COLLECTION AND REPORTING OF SAFETY INFORMATION

All safety information that occur *during* (defined as occurring after patient enrollment until the study completion, or within 30 days of the final dose of Brexpiprazole (Rexulti™) Film-coated Tablet) the study will be documented by the physician. At each visit, the patient will be asked about any symptoms or unexpected occurrences since the last visit. All safety information, regardless of severity or relationship to the Brexpiprazole (Rexulti™) Film-coated Tablet will be reported by the physician to the OPPI using the AE Form (Otsuka Global PV Safety Information Reporting Form in Annex III) immediately or within 24 hours.

3.3. RECONCILIATION OF SAFETY INFORMATION

Reconciliation of Adverse Event between the Safety Database and the study database (or safety database if study database is not obtainable) will be performed annually every 10th business day of December and at the end of the study.

